1. INTRODUCTION

Basic life support (BLS) skills are essential in the care of cardiac arrest victims, but unfortunately only a minority of cardiac arrest victims receive bystander or first responder cardiopulmonary resuscitation (CPR) (1, 2). For cardiac arrest victims the quality of CPR delivered by healthcare professionals is critical, because poor compliance with recommended guidelines has been associated with lower survival rates (3, 4). Healthcare professionals usually receive their first training in BLS in the beginning of their professional education, but the long-term retention of their learning is a more important outcome parameter than learning assessed at the time of the training (1). There is insufficient evidence to recommend the optimal interval or method for BLS retraining (1, 2), however there is low-quality evidence of skills decay within 3 to 12 months after BLS training (5-7) and evidence that frequent training improves responder confidence (5, 8) and willingness to perform CPR (8).

Traditional BLS training is given in groups of various sizes, with one or more instructors. It has been shown that groups of three, five, and eight students do equally good in a post-test, however the group with eight students had significantly less hands-on time, asked fewer questions, conducted more unrelated conversations and ranked themselves lower in self-assessment than groups of three(9). A alternative method to teach BLS is via computer and/or video. Students in a computer-based learning BLS course have been shown to perform with a significantly higher accuracy rate on 60 chest compressions, 12 ventilations and 3 cycles of CPR than students in an instructor-led group (10), and another study showed that skills acquired in a self-learning station combining video-instruction with training using voice feedback were not inferior to instructor-led training (11).

The advantages of self-learning compared to instructor-led training are many. When no instructor is needed, the training can take place when it fits the student best; the student only needs a computer and a manikin. Retraining can take place more often because a course does not have to be planned, and salary for the instructor is saved. The disadvantage of self-learning is the lack of feedback from an instructor, but with voice feedback from the manikin, the student receives feedback regarding the quality of the CPR. The manikin assesses compression depth, correct hand position, correct decompression, compression rate, respiratory volume, respiratory frequency, gastric ventilation (12) and gives voice feedback on those parameters.

A method to assess the quality of CPR is by using the Resusci Anne SkillReporter™ (Laerdal Medical, Stavanger, Norway). The Resusci Anne SkillReporter™ (LSR) is an adult CPR training manikin that focuses on student performance through printed reports on ventilation and compression

compliance. Regarding ventilation trainees obtain measurements on ventilation volume, number of ventilations per minute, overall ventilation volume, number of ventilations, percentage of correct ventilations, number of ventilations with too much volume, number of ventilations with too little volume, number of ventilations that were too fast, and the relation between ventilations and compressions. Regarding compression the Resusci Anne SkillReporter gives feedback on compression depth, number of compressions per minute, compression frequency, total number of compressions, percentage of correct compressions, number of compressions that were too deep, number of compressions that were too shallow, incorrect hand position, incorrect decompression. Another method to assess the CPR is to check if all steps in the CPR-algorithm are fulfilled. A BLS/AED provider assessment record is available via the European Resuscitation Council(13) (fig.2).

Mini Anne CPR & AED (Laerdal Medical, Stavanger, Norway) is a manikin developed to train CPR skills. This innovative self-directed learning programme allows people to learn the core skills of CPR and automatic external defibrillation (AED) use in 30 minutes. The Mini Anne CPR & AED kit instructs the user in a 'practice-while watching' format with the aid of a 30 minute instructional DVD, and a personal, inflatable manikin with an integrated adult/child compression clicker¹. The first year medical students from Bern University Hospital use this manikin in their obligatory BLS course integrated in their first aid training. After a short introduction to the course they train CPR skills for 30 minutes with the Mini-Anne supervised by the instructor. After the training the course continues with four different scenarios. The duration of the first aid course is three hours.

In the "2015 International Consensus on Cardiopulmonary Resuscitation and Emergency Care Science with Treatment Recommendations"(1) it was stated that there was a knowledge gap regarding the skill performance in actual resuscitations of students receiving self-instruction courses when compared with those receiving traditional courses (1). To expand our knowledge we wish to investigate whether there is a difference in the BLS skills in first year medical students directly after training and four months later, when randomly assigned to self-learning versus instructor-led training courses. Our 0-hypothesis is that the students in the self-learning group will not be inferior to the students in the instructor-led group.

2. AIM OF STUDY

The aim of this study is to investigate whether self-learning versus instructor-led learning results in the same BLS skills in first year medical students directly after training and four months later.

¹ <http://www.laerdal.com/gb/MiniAnne#/Info>

3. HYPOTHESIS

Our 0-hypothesis is that the students in the self-learning group will demonstrate the same BLS skills as students in the instructor-led group. The alternative hypothesis is that there will be a difference in the BLS skills demonstrated by the self-learning group compared to the instructor-led group.

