5. PROJECT DESIGN

5.1. Type of research and general project design

This is a randomized controlled trial investigating whether self-learning versus instructor-led learning results in the same BLS skills in first year medical students directly after training and four months later.

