9. STATISTICAL METHODOLOGY

9.1. Determination of Sample Size

Based on a pilot study with 14 participants we calculated a median of 84% correct compressions. The interquartile range was 47% to 93%. We have discussed in the study group that a 20% decrease in percentage of correct compressions would have a clinically impact. Therefore, using a two-sample proportion test with a significance level α of 0.05 and an effect size of 20% (from 64% to 84%) we calculate that it requires 150 subjects to reach a power of 80%. To compensate for drop-outs, we aim to include 200 participants in the study.

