9.2. Planned analysis

All data will be summarized for each individual and a summary of all study participants will be computed. Data will be presented as mean (SD) or %.

Parametric data will be compared by a Students-t test, non-parametric by Mann-Whitney-U test. A $p < 0.05$ is considered as statistically significant.

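### The aim needs a finding of equal or non-inferior skills, but the plan states two conflicting nulls and provides only a difference test, with no margin or confidence interval

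*Combined protocol and SAP*

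**What the plan says.** The null hypothesis is stated twice, differently. Section 1 (Introduction): "Our 0-hypothesis is that the students in the self-learning group will not be inferior to the students in the instructor-led group". Section 3 (Hypothesis): "Our 0-hypothesis is that the students in the self-learning group will demonstrate the same BLS skills as students in the instructor-led group", with a difference between the groups as the alternative. In section 1, the sentence before the non-inferiority null says "we wish to investigate whether there is a difference in the BLS skills".

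The question is framed as sameness in section 2, "The aim of this study is to investigate whether self-learning versus instructor-led learning results in the same BLS skills", and again in section 5.1, "This is a randomized controlled trial investigating whether self-learning versus instructor-led learning results in the same BLS skills". Section 11 makes equal and maintained skills the basis for wider self-training.

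Section 9.1 sizes the trial with a two-sample proportion test (64% against 84%, α 0.05, 80% power, 150 participants, 200 to be recruited). The study group's view there is that "a 20% decrease in percentage of correct compressions would have a clinically impact"; the figure serves as the effect size and is not called a margin.

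Section 9.2 says "Data will be presented as mean (SD) or" percentages, and "Parametric data will be compared by a Students-t test, non-parametric by Mann-Whitney-U test", with p < 0.05 as significant. No non-inferiority or equivalence margin, between-group estimate or confidence-interval rule appears anywhere.

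**The concern.** The two nulls are different hypotheses, and the one in section 1 is also the wrong way round. A non-inferiority test places inferiority by at least the margin in the null, so that rejecting it supports the claim.

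Under section 3, sameness is the null. Failing to reject a null does not establish it, because a small p-value shows a difference while a large one may reflect either similarity or imprecision. The outcome that would justify more self-training is therefore the one the planned analysis cannot demonstrate. The plan does not say that p > 0.05 will be read as sameness, but it offers no other route to that conclusion and does not exclude the reading.

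**Working it through.** **Inputs.** From section 9.1: 64% and 84%, α 0.05, power 80%, 150 needed, 200 recruited, pilot (14 participants) median 84% and interquartile range 47% to 93%. Assumptions: 1:1 allocation (75 or 100 per arm), and an SD for percentage of correct compressions derived from the pilot.

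**1. The plan's own figure.** Pooled two-proportion formula, two-sided, mean proportion 0.74:

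n = [1.96·√(2·0.74·0.26) + 0.842·√(0.64·0.36 + 0.84·0.16)]² / 0.20² = 74.3, so 75 per arm and 150 in total.

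This reproduces the stated 150. The one-sided version gives 118. The trial is thus sized as a two-sided test for a difference, in line with section 3 and not with the non-inferiority sentence in section 1.

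**2. SD.** (93 − 47)/1.349 = 34.1 points. This normal conversion is rough for 14 skewed values. Distributions fitted to the pilot quartiles give about 30 (29.7 piecewise-linear, 30.8 beta). A range of 25 to 40 is carried through.

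**3. Precision.** Half-width of the 95% CI = t(0.975; 2n − 2)·SD·√(2/n). At SD 34.1: 1.976 × 5.57 = 11.0 points with 75 per arm, and 1.972 × 4.82 = 9.5 with 100 per arm.

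**4. Chance that a true 10-point deficit is non-significant** (noncentral t, two-sided 0.05), beside the half-widths:

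| SD | Half-width, 75 / 100 per arm | Non-significant, 75 / 100 per arm |
|---|---|---|
| 25 | 8.1 / 7.0 | 32% / 20% |
| 30 | 9.7 / 8.4 | 47% / 35% |
| 34.1 | 11.0 / 9.5 | 57% / 46% |
| 40 | 12.9 / 11.2 | 67% / 58% |

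These figures show only that p > 0.05 is weak evidence of sameness. They are not error rates against a 20-point margin.

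**5. What a non-significant result can look like at SD 34.1.**
- 75 per arm, observed deficit 10 points: −10 ± 11.0, CI about −21 to +1. Non-significant, and a 20-point decrease is not excluded.
- 100 per arm, observed deficit 9 points: −9 ± 9.5, CI about −18.5 to +0.5. Non-significant; excludes 20 points but not 15.

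The p-value does not separate these two cases; an interval read against a fixed margin does.

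**6. If a margin M were set.** Non-inferiority power with truly equal arms = 1 − F(t(0.975; 2n − 2)), where F is the noncentral t distribution with noncentrality M/(SD·√(2/n)):

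| Margin | SD 34.1, 75 / 100 per arm | SD 40, 75 / 100 per arm | n per arm for 80% at SD 34.1 (SD 25 to 40) |
|---|---|---|---|
| 20 | 95% / 98% | 86% / 94% | 47 (26 to 64) |
| 15 | 76% / 87% | 63% / 75% | 83 (45 to 113) |
| 10 | 43% / 54% | 33% / 42% | 184 (100 to 253) |

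**The case against.** The strongest reply is that sections 3, 9.1 and 9.2 form one coherent two-sided difference test, and that the outlier is a single background sentence in section 1. Asking whether skills are the same can be read as asking whether they differ, and section 11 is a conditional benefit statement, not a decision rule. All of that is fair. It shows which hypothesis the calculations follow, but it supplies no way to reach the conclusion that sections 2, 5.1 and 11 look for.

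There is also a numerical reply. A non-significant result has a lower limit above minus twice the half-width, so whenever the half-width is below 10 every non-significant result excludes a 20-point deficit. That holds with 100 per arm up to an SD of about 35.9, and with 75 per arm up to about 31. The primary test follows training directly, so close to 100 per arm is realistic. At SD 34 a true 20-point deficit is missed only 5.4% (75 per arm) or 1.5% (100 per arm) of the time, and at SD 30 both examples in step 5 become significant.

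This is correct, and it limits the examples to the stated SD. But the argument itself needs an interval that section 9.2 does not report and a margin that no section names. It also fails at SD 40 (14% and 6% missed) and says nothing about stricter margins.

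Finally, section 11 also requires skills to be maintained, so a rule for the immediate test alone would not settle that part. This stands.

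**Conclusion.** The concern holds and must be fixed. Sections 1 and 3 contradict each other, and following section 9.2 exactly would leave a non-significant primary result unable to answer the stated aim. That logical defect needs no assumed SD.

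The size of the gap does depend on one. It rests on a two-sample t model, 1:1 allocation and an SD near 34 taken from 14 skewed pilot values. The chance that a real 10-point deficit is non-significant lies between 20% and 67% across SD 25 to 40 and 75 to 100 per arm. The documents do not call 10 points important, so this measures imprecision, not clinical error. The fault lies in the hypothesis and decision rule, and not necessarily in the sample size.

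**What to change.** Reconcile sections 1 and 3 into one hypothesis. In section 9.2, make the primary analysis the mean difference in percentage of correct compressions (self-learning minus instructor-led) directly after training, with a two-sided 95% CI. A robust or bootstrap standard error would suit the skew, with Mann-Whitney as a sensitivity analysis. Then choose one of two routes.

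- **(a) Non-inferiority.** The null is that self-learning is worse by the margin or more. The study group justifies the margin and fixes it before any outcome data are examined. Non-inferiority is concluded only if the lower limit lies above minus the margin, and section 9.1 states the power at that margin. The study group already regards a 20-point decrease as clinically important, so 20 is the largest margin that could be defended, and is not automatically an acceptable loss.
- **(b) Difference test.** Keep section 3, delete the non-inferiority sentence in section 1, reword the aim (sections 2 and 5.1) as estimating the difference, and state that p > 0.05 will not be read as the same or not inferior.

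Under either route, report the four-month comparison with its own interval, since the immediate test cannot speak to retention.

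The cost is wording in sections 1, 2, 3, 5.1, 9.1 and 9.2, with no new data. Under (a) the planned size is enough at 20 points, borderline at 15, and too small at 10 if the SD is near 34. If a stricter margin is chosen, the lower power should simply be stated. Under (b) no participants are added, but any claim of sameness or non-inferiority is given up.

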4. OBJECTIVES AND OUTCOMES

4.1. Objectives

The objective of this study is to compare the BLS skills measured by the percentage of correct compressions achieved directly after BLS skills training in a self-learning group compared to an instructor-led group using the printed report from the LSR and the score on the standardized ERC BLS/AED provider assessment record(13) (fig.2). Another objective is to investigate the degree of competence loss after four months.

4.2 Outcomes

Our primary outcome will be the percentage of correct compressions obtained from the printed report from the LSR. With this parameter we will compare the two groups directly after the first teaching session.

Our secondary outcomes are:

- The subcomponents of the printed report from the LSR (ventilation volume, number of ventilations per minute, overall ventilation volume, number of ventilations, percentage of correct ventilations, number of ventilations with too much volume, number of ventilations with too little volume, number of ventilations that were too fast, the relation between ventilations and compressions, compression depth, number of compressions per minute, compression frequency, total number of compressions, percentage of correct compressions, number of compressions that were too deep, number of compressions that were too shallow, incorrect hand position, and incorrect decompression).
- The score on the BLS/AED provider assessment record(13) (fig.2).
- Degree of loss of competence after four months for all the primary and secondary outcomes.
- Influences of gender and prior BLS training will also be investigated, as well as the decay of competences.

5. PROJECT DESIGN

5.1. Type of research and general project design

This is a randomized controlled trial investigating whether self-learning versus instructor-led learning results in the same BLS skills in first year medical students directly after training and four months later.

5.2. Procedures

When participants attend the “Erweiterte Erste Hilfe für Studierende der Humanmedizin” they will receive a short introduction about the study. We will invite all first year students to participate in the study. As the study is voluntarily, participants will need to sign a written informed consent. After that we will randomize the students to either group A or Group B (see figure 1). Group A will train their technical CPR-skills with supervision by a tutor (either general practitioner or medical student, all trained in CPR teaching) and group B will train without supervision. The participants in group B will not be allowed to communicate with each other during the training. The training will take about 40 minutes for each group. Directly after the training each group will be tested and the printed report form from the LSR will be obtained for each participant. In the test the students will perform CPR in a simulated scenario as a first responder. The scenario is: “A male person has collapsed in the hall of the university and you cross by. No other persons are present at the moment.” The participant should start CPR as learned in the training. During the CPR a departmental research fellow will observe the study participants and record BLS/AED actions on a scoring sheet.

To avoid struggle with the equipment, each student will be given two minutes to familiarize themselves with the testing manikin and the equipment (an AED). We will record three cycles of two minutes CPR (with five times 30:2 compression : ventilation intervals, as recommended by the current international resuscitation guidelines) (14). During the three cycles an AED will be delivered and the study participant has to apply the AED and deliver a shock – after that the study terminates. After the BLS/AED competence testing, both groups will continue the rest of their first aid course together and the first part of the study ends. Four months later we will repeated the same scenario over the same time interval and record the same parameters. At the end of the second testing, a short feedback will be provided on the BLS/AED competence and further practice will be provided to the students to improve their CPR competence. From this point forward no further data will be collected

[figure not shown]

Figure 1: Procedure

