6. METHODS OF MINIMISING BIAS

6.1. Randomization

We will use a computerized randomization list (www.randomization.com) using block randomization of 10 to assure proper distribution during each group of students.

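### Only the instructor-led arm has tutors, and section 9.2 allows for neither tutor clustering nor course session, so the type I error may differ from 5%

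*Combined protocol and SAP*

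**What the plan says.** Students are randomized one by one (section 5.2): "After that we will randomize the students to either group A or Group B". The arms then differ in who is present during training. For the instructor-led arm: "Group A will train their technical CPR-skills with supervision by a tutor", who is a general practitioner or a medical student, in either case trained to teach CPR. For the self-learning arm, which has no supervision: "The participants in group B will not be allowed to communicate with each other during the training".

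Section 6.1 describes the allocation list as "using block randomization of 10 to assure proper distribution during each group of students". I read this as blocking within each course group. The allocation ratio is not stated, and I assume 1:1.

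Section 9.2 gives the whole comparison: "Parametric data will be compared by a Students-t test, non-parametric by Mann-Whitney-U test", at p < 0.05. Section 9.1 sizes the trial with an ordinary two-sample proportion test. No section mentions tutor effects, sessions, clustering, an ICC, a mixed model or robust standard errors. The variables listed in section 8.3 include neither the tutor nor the session. The number of tutors, the students per tutor and the way students are assigned to tutors are not given.

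**The concern.** The tutor is the difference between the arms. Tutors may be general practitioners or medical students, and some will teach better than others. If one tutor teaches several group A students, those students share that tutor's strengths and weaknesses. Randomizing individuals does not remove this correlation, because it arises after allocation. Group B has no counterpart, so the design is partially nested.

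A test that assumes independent students leaves the between-tutor part out of the standard error. The primary comparison, percentage of correct compressions directly after training, could then reach p < 0.05 too often. This matters if the conclusion is about instructor-led teaching in general rather than about the tutors who happened to teach this course. Section 11 presents the findings as generalizable to health care systems worldwide, which is the wider target.

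**Working it through.** **The plan's own figure.** Section 9.1 gives 64% against 84%, alpha 0.05 and 80% power. Two-sided testing is not stated there, but the alternative hypothesis in section 3 implies it. With pooled variance and no continuity correction:

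n per arm = [1.96·√(2·0.74·0.26) + 0.842·√(0.64·0.36 + 0.84·0.16)]² / 0.20² = (1.216 + 0.508)² / 0.04 ≈ 74.3, so 75 per arm and 150 in total. This matches the plan and assumes independent students.

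**Effect of tutor clustering in group A.** Assumptions: m students per tutor, tutor ICC ρ in group A, equal arms, equal total variance, tutors regarded as a sample from a wider pool. Neither m nor ρ is in the documents.

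- Design effect in group A: DE = 1 + (m − 1)ρ
- True SE / planned SE: r = √[(1 + DE)/2]
- Actual two-sided alpha: 2·[1 − Φ(1.96/r)]

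| m | ρ | DE | r | actual alpha |
|---|---|---|---|---|
| 5 | 0.01 | 1.04 | 1.010 | 5.2% |
| 5 | 0.05 | 1.20 | 1.049 | 6.2% |
| 5 | 0.10 | 1.40 | 1.095 | 7.4% |
| 5 | 0.20 | 1.80 | 1.183 | 9.8% |
| 10 | 0.01 | 1.09 | 1.022 | 5.5% |
| 10 | 0.05 | 1.45 | 1.107 | 7.7% |
| 10 | 0.10 | 1.90 | 1.204 | 10.4% |
| 10 | 0.20 | 2.80 | 1.378 | 15.5% |

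With ρ = 0 alpha is 5.0% for any m. Simulation with 100 per arm (10,000 runs) agrees for both planned tests: at ρ = 0.10 the t-test gave 7.5% (m = 5) and 10.7% (m = 10), and Mann-Whitney 7.2% and 10.4%.

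**Effect of sessions shared by both arms.** Let s be the share of total variance due to course session, with the arms balanced within session. Session effects then cancel in the difference between arms but still inflate the planned SE, so

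r² = 1 + (m − 1)ρ/2 − s.

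The two errors cancel only when s = (m − 1)ρ/2:

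- m = 5, ρ = 0.05: s = 4·0.05/2 = 0.10. Simulated alpha with 10% session variance was 5.0%; with 20% it was 4.2%.
- m = 5, ρ = 0.01: s = 4·0.01/2 = 0.02. With 10% session variance the simulated alpha was 4.3%, so the test was conservative.
- m = 10, ρ = 0.10: s = 9·0.10/2 = 0.45. With 10% and 20% session variance the simulated alpha was still 8.7% and 8.0%.

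**Power.** Scaling the plan's calculation, n per arm = 75·(1 + DE)/2. At m = 5, ρ = 0.01 this is 76.5, so 154 in total. At m = 10, ρ = 0.10 it is 108.75, so 218. However, section 9.1 treats a per-student percentage as a proportion. On a comparison of means, with SD = (93 − 47)/1.349 = 34.1 points (normality assumed, although the pilot quartiles look skewed) and a 20-point difference, 75 per arm gives 94.9% power with independent students and 74.1% at m = 10, ρ = 0.20. With 100 per arm the latter is 85.3%.

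**The case against.** The strongest objection is that inflation is not established. Some features point to a small ICC: the primary outcome is printed by a manikin, all tutors are trained in CPR teaching, and section 1 describes the existing course as built around a video-guided kit. At ICC 0.01 the excess is 0.2 to 0.5 percentage points, and a modest session effect turns the test conservative. This stands, and it rules out saying that the standard error is too small or that 5% is exceeded. A reader might infer that from the design, but the documents do not contain the figures needed.

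A second objection is that inflation requires tutors to be treated as a random sample. With these tutors held fixed, simulated alpha was 4.3% to 5.1% (5 and 10 students per tutor, ICC 0.01 to 0.10). That is correct. The wider target is nevertheless the one section 11 claims, so allowing for tutors is reasonable.

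Third, that a tutor teaches several students together is an inference from references to groups. Five per tutor is half a randomization block under 1:1 allocation, not a stated teaching-group size.

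Two further readings go too far:

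- *A claim that the arms are the same becomes too easy.* Under section 3 sameness is the null and section 9.2 has only p < 0.05, so an understated SE produces more rejections and makes that claim harder. The reading would fit an interval set against a margin. Section 1 mentions non-inferiority, but the plan gives no margin and no interval.
- *The trial is underpowered.* Over the assumed range, the comparison of means falls below 80% power only at 10 students per tutor and ICC 0.20 with 75 per arm, and not with 100 per arm.

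**Conclusion.** The structural point holds. Tutors are nested in one arm only, and the planned tests use neither tutor nor the course groups that the blocking aims to balance. For inference beyond these tutors, the type I error **may** exceed 5%: from about 5.2% to 15.5% for 5 to 10 students per tutor and ICC 0.01 to 0.20, without a session effect. Ignored session effects act in the opposite direction, and at low ICC they can bring the error rate to 5% or below. The direction of the net error is therefore unknown, and the planned test is calibrated only by coincidence. These figures rest on an assumed ICC and group size, equal arms and equal total variance.

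The point concerns the comparison directly after training. At four months the structure differs, because both arms take the rest of the course together. I rate this a cheap improvement, not a flaw that invalidates the comparison.

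**What to change.** 1. State the number of tutors, the size of the teaching groups and how students are assigned to tutors.
2. Record the tutor (group A) and the course session (all students).
3. In section 9.2, make the primary analysis one that includes session as a stratum and allows for tutor clustering in group A. This can be a partially nested mixed model with a tutor random effect in group A only, or cluster-robust standard errors. Either needs a small-sample correction, since tutors may be few.
4. Keep the unadjusted comparison as a sensitivity analysis, including Mann-Whitney, because the outcome is bounded and the pilot suggests skew (median 84%, quartiles 47% and 93%).
5. Report the tutor ICC with its uncertainty.

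The cost is one or two data fields and a few lines of text. The confidence interval may be wider, by a factor of about 1.0 to 1.4 over the assumed range. If the ICC is near zero, little is lost and the report shows it. If tutor identity is not recorded, the question may be impossible to answer later.
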